2.3.2. Secondary Hypotheses

- 1. Subjects wearing the JJVCI Investigational contact lenses on a daily wear basis will have patient reported handling at the 2-Week Follow Up visit that is non-inferior to that of subjects wearing predicate device on a daily wear basis. A non-inferiority margin of -5 CLUE points will be used.
- 2. Subjects wearing the JJVCI Investigational contact lenses on a daily wear basis will have patient reported vision at the 2-Week Follow Up visit that is non-inferior to that of subjects wearing predicate device on a daily wear basis. A non-inferiority margin of -5 CLUE points will be used.

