### 4.2. Secondary Hypotheses

- 1. Subjects wearing the JJVCI Investigational contact lenses on a daily wear basis will have patient reported handling at the 2-Week Follow Up visit that is non-inferior to that of subjects wearing predicate device on a daily wear basis. A non-inferiority margin of -5 CLUE points will be used.
- 2. Subjects wearing the JJVCI Investigational contact lenses on a daily wear basis will have patient reported vision at the 2-Week Follow Up visit that is non-inferior to that of

subjects wearing predicate device on a daily wear basis. A non-inferiority margin of -5 CLUE points will be used.

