# 7.4. Sample Size Justification

This study was designed and powered to show non-inferiority of the Test lens compared to the Control lens with respect to logMAR Visual Acuity, Slit Lamp Findings (Grade 3 or higher) and CLUE comfort. It was assumed there was no difference between the Test and Control lens with respect to slit lamp findings and a 1 letter difference (0.02) between the Test and Control lenses with respect to visual acuity logMAR. Based on data from 3 historical studies, it was assumed there was a 2-point difference between the Test and Control lenses with respect to CLUE comfort based on the summary statistics from the first period of the historical studies.

In addition to the endpoints mentioned above this study was also powered to demonstrate noninferiority of the Test lens relative to the Control lens with respect to vision satisfaction in bright lighting and the proportion of eyes with acceptable fitting while the Test lens is significantly superior to 90%.

Unless otherwise specified, the sample size was calculated to achieve a minimum statistical power of 80% and a type I error of 5%.

A total of 5 historical studies were utilized in the sample size calculation. Table 5 displays the studies, their corresponding study design and the number of subjects enrolled and completed perprotocol.

			No.	No. Completed
Study	Study Design	Endpoints Collected	Enrolled	Per-Protocol
	2X3 Crossover	CLUE, SLF Lens Fit	135	132
	2X3 Crossover	CLUE, Visual Acuity (logMAR), SLF, Lens Fit	133	121
	2X3 Crossover	CLUE, SLF Lens Fit	92	78
	Single-Arm	SLF, Lens Fit	54	48
	Single-Arm	SLF, Lens Fit	56	41

Table 5: Historical Studies Included in Sample Size Calculation

CLUE Domain [Mean(SD)  ]	Test	Control

Comfort	66.66 (21.066)	63.90 (24.197)
Handling	69.32 (18.454)	71.11 (20.429)
Overall Quality of Vision	64.49 (17.221)	64.44 (23.351)

SD = Standard Deviation

Table 7: Descriptive Summary of Visual Acuity (logMAR) - 2-Week Follow-up Evaluation-Period 1 Only

Visual Acuity High Illumination High Contrast	Test	Control
[Mean(SD)  ]	-0.088 (0.0862)	-0.0622 (0.0740)

SD = Standard Deviation

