#### Slit Lamp Findings

There were no Grade 3 or higher SLFs observed in any of the historical studies. Assuming no difference between study lenses and a correlation 0.70 between left and right eyes within the same subject (intra-subject correlation), a reference rate of no more than 5% was assumed (worse-case scenario) with a non-inferiority odds ratio margin of 2. A total of 2000 replicating trials were simulated, each replicated sample was analyzed using a generalized estimating equation (GEE) model with a binary distribution and the logit as the link function. Each model included lens type as the only fixed, eye was included as a random effect. The Odds ratio and corresponding 95% confidence interval was used estimate differences between the Test and Control lenses. The upper limit of each 95% confidence interval was compared to 2; if the upper limit was below 2 then NI=1; otherwise NI=0. Statistical power was calculated at the average NI. A sample size of 224 (112 per arm) was chosen to achieve a minimum statistical power of 80%.

Using a reference rate for the control that does not exceed 5% and no more than a 5% difference between the Test and Control lenses translates to an odds ratio margin of 2. A reference rate of 5% was used since this is the worst-case scenario.

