#### Vision Satisfaction

Vision satisfaction in bright lighting sample size estimate was calculated using historical data One-thousand boot strap samples were simulated based on the historical data. For each replicated sample a generalized linear mixed model was used with a multinomial distribution and the cumulative logit as the link function. Lens wear was included in the model as the only fixed effects.

Using a reference rate of 0.50 for the Control lens and assuming no difference between the Test and Control a 10% difference translate to a cumulative odds ratio margin of 0.67. the reference rate of 0.50 was used since this is considered to be the worst-case scenario.

	Number per Subjects to	
Endpoint	Complete	Power
Distance Monocular Visual Acuity (logMAR)	30	86%
SLFs (Grade 3 or Higher)	224	80%
Acceptable lens Fit	100	82%
CLUE Comfort	224	87%
Vision Satisfaction in Bright Lighting	40	87%

Table 11: Sample Size Estimates and Power	Calculations for Primary Endpoints
---	------------------------------------

Table12: Sample Size Estimates and Power Calculations for Secondary Endpoints

Endpoint	Number per Subjects to Complete	Power
CLUE Handling	224	63%
CLUE Overall Quality of Vision	224	71%

As indicated in Table 10 and 11 above, the sample size chosen for this study was primary driven by Slit Lamp Findings (Grade 3 or higher) and CLUE Comfort. The plan is to enroll 236 eligible subjects (118 subject per arm) with a target of 112 subjects to complete each arm in the study. During the enrollment period, the subject drop-out rate with be closely monitored, if an unexpectedly high dropout rate is observed, then the targeted total enrollment number maybe be increased accordingly to ensure that a minimum of 224 subjects complete the study.

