#### Hypothesis Testing

The null and alternative hypotheses for CLUE comfort non-inferiority of the Test lens relative to the Control lens are as follows:

$$\begin{array}{l} H_0: \ \beta_1 \le -5 \\ H_A: \ \beta_1 > -5 \end{array}$$

Non-inferiority will be declared if the lower bound of the 2-sided 95% credible interval of the difference between the Test lens and the Control lens is greater than -5, i.e.,  $P(\beta_1 > -5) \ge 0.975$ .

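### The stated power for CLUE handling (63%) and CLUE vision (71%) is printed without inputs and is not reached under the planned 2-sided 95% rule with the historical SDs, unless baseline adjustment is strong

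*SAP*

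**What the plan says.** In the table headed "Sample Size Estimates and Power Calculations for Secondary Endpoints" (SAP 7.4, Table 12; same values in protocol 14.2), the two rows read "CLUE Handling 224 63" and "CLUE Overall Quality of Vision 224 71", the last number in each being a percentage. The 224 is the total for both arms: "A sample size of 224 (112 per arm) was chosen to achieve a minimum statistical power of 80" (SAP 7.4, slit lamp findings).

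The handling hypothesis is "patient reported handling at the 2-Week Follow Up visit that is non-inferior to that of subjects wearing predicate device on a daily wear basis" (SAP 4.2). For handling and for vision alike, "A non-inferiority margin of -5 CLUE points will be used" (protocol 2.3.2).

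SAP 10.2 sends both endpoints to the comfort method, and SAP 14.2 to the comfort code. For comfort, "Non-inferiority will be declared if the lower bound of the 2-sided 95% credible interval" of the difference lies above -5, equivalently a posterior probability of at least 0.975 (SAP 10.1). The comfort model also has baseline CLUE as a fixed effect.

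The historical Period 1 summary in SAP 7.4 (protocol Table 7) gives mean (SD), Test then Control: "Handling 69.32 (18.454) 71.11 (20.429"). For overall quality of vision it gives 64.49 (17.221) and 64.44 (23.351).

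SAP 7.4 states a 5% type I error for the sample size without saying one- or two-sided. It describes a power method for comfort only: PROC POWER for two means, difference 2, SD 21. Nothing comparable is given for handling or vision.

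**The concern.** A power figure without its difference, SD and alpha cannot be checked. Here three choices matter.

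- **Alpha.** The decision rule works at one-sided 2.5%, but the printed values fall out naturally at one-sided 5%.
- **Difference.** The plan's own history has the Test lens 1.79 points lower on handling.
- **SD.** The Control SD for vision (23.351) is well above the Test SD (17.221), and an SD near 17 is what reproduces 71%.

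The secondary objective rests on these two tests, and the table presents each as more likely to pass than fail. If the real chance is nearer even, or lower for handling, a missed secondary result should be read with that in mind.

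**Working it through.** **Inputs.** n = 112 per arm and margin 5 (SAP 7.4, SAP 4.2). Handling: SDs 18.454 and 20.429, difference 69.32 - 71.11 = -1.79. Vision: SDs 17.221 and 23.351, difference 64.49 - 64.44 = +0.05. Means and SDs are from SAP 7.4.

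**Formula.** SE = sqrt((SD_T² + SD_C²)/112). Noncentrality = (difference + 5)/SE. Power = P(T > t_crit), with T noncentral t on 222 df. t_crit is 1.652 at one-sided 5% and 1.971 at one-sided 2.5%. The one-sided 2.5% test stands in for the credible-interval rule.

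**Step 1: reproduce the printed figures (one-sided 5%, zero difference).**
- Handling, SD 19: SE = 19 × sqrt(2/112) = 2.539; 5/2.539 = 1.969; power 62.5% (printed 63%).
- Vision, SD 17: SE = 2.272; 5/2.272 = 2.201; power 70.9% (printed 71%).
- Variants for handling: the Test SD of 18.454 gives 64.7%; both arms' SDs give 60.7%.
- Variants for vision: the Test SD of 17.221 gives 69.9% at zero and 70.6% at +0.05; both arms' SDs at +0.05 give 58%.

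**Step 2: change only alpha, to one-sided 2.5%.** Handling (SD 19, zero) falls to 50.0%. Vision (SD 17, zero) falls to 59.2%.

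**Step 3: one-sided 2.5% with both historical SDs, unadjusted.**
- Handling SE = sqrt((340.55 + 417.34)/112) = 2.601.
  - At zero: 5/2.601 = 1.922; power 48.2%.
  - At -1.79: 3.21/2.601 = 1.234; power 23.2%.
- Vision SE = sqrt((296.56 + 545.27)/112) = 2.742.
  - At +0.05: 5.05/2.742 = 1.842; power 45.0%.

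**Step 4: allow for baseline adjustment.** Multiply the SDs by sqrt(1 - r²), where r is the correlation of baseline with follow-up score. The documents give no r, so these values are assumptions.

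| r | Handling, 0 | Handling, -1.79 | Vision, +0.05 |
|---|---|---|---|
| 0 | 48% | 23% | 45% |
| 0.3 | 52% | 25% | 49% |
| 0.5 | 60% | 29% | 56% |
| 0.6 | 67% | 34% | 63% |
| 0.7 | 76% | 40% | 73% |

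The printed 63% for handling is reached at r of about 0.55, and only at zero difference. The printed 71% for vision needs r of about 0.68.

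**The case against.** **The inputs are not known.** This stands. Other routes reach each figure separately at one-sided 2.5% with both SDs: handling at +1 gives 63.2%, and vision at +2 gives 72.0%. The historical table shows neither difference for its endpoint, so these are less likely, but they are not excluded. A reader might infer that the planners used the Test-arm SD alone and passed over the Control arm. The documents do not support saying so. No SD is printed, and for handling the Test SD gives 64.7%, not 63%.

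**The planned analysis is adjusted.** This also stands. A reader might take 48%, 23% and 45% as the power of the planned analysis, but they are unadjusted values. With r = 0.6, handling at zero exceeds the printed 63%.

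**The -1.79 is an uncertain estimate.** It is a pooled Period 1 difference printed without a sample size or standard error. The three crossover studies completed 132 + 121 + 78 = 331 subjects. If 100 to 165 per lens contributed (an assumption), the SE is sqrt(757.89/165) = 2.1 to sqrt(757.89/100) = 2.8, so -1.79 is within one SE of zero. Planning at zero difference is common, and this plan does it for slit lamp findings. A reader might conclude that handling is more likely to fail than pass. That holds if -1.79 is the true difference and r is below about 0.78; at zero difference the chance is about even or better once there is modest adjustment.

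**Little turns on these rows.** SAP 7.4 says the sample size was driven by slit lamp findings and comfort, and the two printed powers are already below 80%. This limits the severity. It does not make the figures right.

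**Conclusion.** The point holds in a limited form. The two rows have no stated inputs. On the planned rule with the documents' own SDs, the printed values are reached only if baseline CLUE correlates strongly with follow-up: about 0.55 for handling, and then only at zero difference, and about 0.68 for vision. Unadjusted, the shortfall is about 15 points for handling at zero (63 against 48), 40 points at -1.79 (63 against 23), and 26 points for vision (71 against 45). These figures rest on 112 completers per arm, the historical SDs carrying over, and a normal-theory test standing in for the posterior rule.

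Severity is minor. Confidence in the recomputed powers is high; confidence about which inputs lay behind the printed figures is only moderate.

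**What to change.** In SAP 7.4 (Table 12) and the matching protocol 14.2 table, recompute both rows at one-sided 2.5% with both arms' SDs. Show handling at zero and at -1.79, and vision at +0.05. Print the difference, SDs, alpha and any assumed baseline correlation beside each figure, with a range if the correlation is not known from earlier studies. If the printed 63% and 71% did rest on baseline adjustment or on other differences, say so and give the source.

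The cost is two table rows and a sentence or two in each document, and less favourable stated power. No subjects are added, and no margin, model or decision rule changes.

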## 7.5. Statistical Significance Level

All planned analysis will be conducted with an overall type I error rate of 5%. There will be neither adjustment for multiple tests nor adjustment for multiplicity of endpoints. Unless otherwise specified, all statistical tests will be 2-sided.

## 7.6. Handling of Missing Data and Drop-outs

Missing or spurious values will not be imputed. The count of missing values will be included in the summary tables and listings.

Subject dropout is expected to be one of the main reasons of missing data in this clinical trial. Past clinical trials don't provide the evidence that subject dropout is systematic or not-at-random. To evaluate the impact of missing data, sensitivity analysis may be considered by automatically sampling all missing values and incorporating them in the Markov chain for the parameters using the PROC MCMC procedure.

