8.2. Withdrawal/Discontinuation from the Study

A subject will be withdrawn from the study for any of the following reasons:

- Subject death during the study period
- Subject withdrawal of consent
- Subject not compliant to protocol
- Subject lost to follow-up
- Subject no longer meets eligibility criteria (e.g. the subject becomes pregnant)
- Subject develops significant or serious adverse events causing discontinuation of study lens wear
- Subjects who have experienced a Corneal Infiltrative Event (CIE)
- Investigator's clinical judgment regarding the subject safety reasons (that it is in the best interest of the subject to stop treatment)
- Subject missed a scheduled study visit

- Subject not compliant with study lens wear schedule
- Subject not successfully dispensed due to lack of efficacy and safety including poor vision, poor comfort or unacceptable fit
- Subject out of visit window visit with two or more days

For discontinued subjects, the Investigator will:

- Complete the current visit (scheduled or unscheduled)
- Complete the Final Evaluation, indicating the reason that the subject was discontinued from the study
- Record the spherocylindrical refraction with best corrected distance visual acuity
- Collect used test article(s) (worn or brought to the visit) from the subject
- Collect all unused test article(s) from the subject

An additional subject will be enrolled if a subject discontinues from the study prematurely.

In cases where a subject is lost to follow-up, every possible effort must be made to contact the subject and determine the reason for discontinuation/withdrawal. The measures taken to follow up must be documented including two written attempts and a certified letter (or equivalent) as the final attempt.

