## 5.4. Per-Protocol (PP)

Per Protocol Analysis set will be the primary analysis population. It will include all subjects who have successfully completed all visits and did not substantially deviate from the protocol as determined by the trial cohort review committee prior to database hard lock. Justification of excluding subjects with protocol deviations in the per-protocol population set will be documented in a memo to file.

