# 10. STATISTICAL ANALYSIS

## 10.1. Primary Analysis

Primary efficacy analysis:

All the efficacy analyses will be conducted on PP population. As sensitivity analysis, the efficacy analysis will be repeated on the ITT population

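### The planned missing-data checks cannot reveal bias in the three efficacy endpoints if lens-related loss after randomisation differs by arm

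*SAP*

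**What the plan says.** - **Population.** SAP 10.1: "All the efficacy analyses will be conducted on PP population". SAP 5.4 requires all visits completed and no substantial deviation. SAP 10.1 adds: "As sensitivity analysis, the efficacy analysis will be repeated on the ITT population". Protocol 14.5 says the repeat goes ahead whatever data are missing.
- **Missing data.** SAP 7.6: "Missing or spurious values will not be imputed". It then gives a reason for not expecting trouble: "Past clinical trials don't provide the evidence that subject dropout is systematic or not-at-random". It offers one further check, as an option: "sensitivity analysis may be considered by automatically sampling all missing values", within the same Markov chain as the parameters.
- **Outcome timing.** SAP 10.1 analyses all three efficacy endpoints at the two-week follow-up. SAP 7.2 keeps unscheduled visits out of the efficacy analysis.
- **Order of events.** Protocol 5.1 and SAP 2.4 place randomisation before the first fitting. Under Protocol 7.2 (steps 1.22 and 1.24), a subject can be stopped after wearing the assigned lens for unacceptable fit, acuity worse than 20/30, or feedback such as poor comfort. Protocol 8.2 lists as a withdrawal reason: "Subject not successfully dispensed due to lack of efficacy and safety including poor vision, poor comfort or unacceptable fit". It also provides for discontinued subjects to be replaced.

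**The concern.** Some subjects can leave after randomisation for the very attributes being measured, comfort and vision. They have no two-week value. In a non-inferiority trial, losing dissatisfied Test wearers while keeping comparable Control wearers favours success. Comfort, logMAR and bright light must all pass (SAP 4.1).

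A plan may use per-protocol as primary if a second analysis would expose this problem. Here neither the ITT repeat nor the optional sampling can do so, although SAP 7.6 offers the sampling for that purpose. Because discontinued subjects are replaced, reaching 224 completers gives no assurance on the point.

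**Working it through.** **1. Who is missing from each analysis.** A subject stopped at Visit 1 has no CLUE follow-up score, no two-week bright-light item and no ETDRS logMAR value. The Final Evaluation (Protocol 7.2) and the unscheduled-visit procedures (Protocol 7.3) collect none of these. The subject is outside PP. The subject may count as ITT, which asks for at least one recorded observation, but contributes no efficacy outcome. ITT differs from PP only through subjects who have a two-week value and were excluded for deviations.

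**2. What the optional sampling does.** The coded comfort likelihood (SAP 14.1) is normal, with mean given by lens, baseline, age, sex and site. There is no selection or shift term. For any such model, ∫ p(y_obs, y_mis | θ) dy_mis = p(y_obs | θ). The posterior for θ, including β1, is therefore the same with or without the sampling step, apart from Monte Carlo error. The same argument covers the other two endpoints.

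A numerical check used the SAP's comfort model and priors with SD 21 and 116 per arm on one simulated data set with a true difference of −5. Site, age and sex were omitted, and a baseline correlation of 0.5 was assumed.

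| Data | β1 (95% credible interval) |
|---|---|
| Full data | −2.37 (−6.85 to 2.10) |
| 4 lowest Test and 4 random Control missing, observed cases | −1.03 (−5.36 to 3.30) |
| Same, missing values sampled | −1.01 (−5.29 to 3.34) |
| Lowest 15% of Test missing, observed cases | 1.78 (−2.56 to 6.09) |
| Same, missing values sampled | 1.81 (−2.63 to 6.14) |

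In the 15% case both planned routes pass the −5 margin and the full data do not.

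**3. Size at the planned loss.** The SAP gives no figure for the effect of dropout, so there is none to reproduce. SAP Table 2 plans 116 randomised and 112 completed per arm: 4/116 = 3.4%.

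- *Bright light.* Historical Test satisfaction (SAP Table 10) is (72 + 129)/242 = 83.1%. If the four lost Test subjects would all be unsatisfied and Control loses none, the shift is 4/116 × 83.1 = 2.9 points of 10.
- *Comfort.* If those lost would score d points below completers, the shift is 4/116 × d: 0.7 points for d = 20 and 1.0 for d = 30. Both values of d are assumptions.
- *Headroom for comfort.* With the SAP 7.4 inputs (+2, SD 21, 112 per arm), the unadjusted half-width is 1.96 × 21 × √(2/112) = 5.5. The expected lower limit is 2 − 5.5 = −3.5, which leaves 1.5 points. Baseline adjustment would increase that.
- *Equal loss.* For bright light, with historical Control satisfaction of (51 + 130)/242 = 74.8%, the net shift is 4/116 × (83.1 − 74.8) = 0.3 points. For comfort, the bias is zero if f and d are the same in both arms.

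**4. Size at a higher Test loss.** SAP Table 5 totals 470 enrolled and 420 completed per-protocol: 50/470 = 10.6%. Comfort then shifts by 0.106 × 20 = 2.1 to 0.106 × 30 = 3.2 points.

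**5. Error rate.** These are 10,000 simulated trials per scenario at a true difference of −5, with the same SD and assumed correlation. A least-squares 95% limit stands in for the credible limit; nominal error is 2.5%. With Test dropouts 20 points below completers and 3.4% random Control loss, false non-inferiority was 5.0%, 13.2% and 23.6% for Test loss of 3.4%, 10.6% and 15.2%. With 3.4% lost in both arms, it was 2.5% if the loss was random and 3.0% if each arm lost its lowest scorers.

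**The case against.** The strongest reply is that nothing in the documents shows loss will differ by arm. The withdrawal rules are the same for both lenses. Historical comfort (66.66 against 63.90) and bright-light satisfaction (83.1% against 74.8%) favour Test, and no unacceptable fits were recorded. At the planned loss, even the one-sided scenarios are small against the margins. All of this stands. It bears on how likely the bias is, not on whether the planned checks could find it.

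Three stronger readings are tempting and are not supported:

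- **A reader might infer that 10.6% is the dropout to expect.** That figure runs from enrolment to per-protocol completion. It may include screen failures and deviation exclusions, three of the five studies were crossovers, and losses are not given by lens. It serves only as an upper illustration.
- **A reader might infer that investigators will know the lens when they decide on continuation.** Protocol 5.2 says investigators are difficult to mask but ties the visible difference to activation by outdoor light. The Visit 1 decision follows fitting in the clinic. Differential loss is possible, not established.
- **A reader might infer that every primary endpoint is affected.** Fit and slit lamp findings are analysed on the safety population, and fit is recorded at Visit 1, so early fit failures count there.

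The SAP also reports missing counts and discontinuation reasons, so loss is not hidden. Its effect on the conclusion is what goes untested. Finally, the SAP does not use the term missing at random. That assumption is inferred from the absence of any missingness model.

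**Conclusion.** The point holds for comfort, logMAR and bright light. The optional sampling cannot change the lens-effect posterior, and the ITT repeat tests deviation exclusions rather than dropout. Neither can detect bias from lens-related loss that differs by arm. This does not show that the trial will be biased.

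The sizes above are scenarios, not estimates. They rest on loss being wholly lens-related and informative only in Test, and for comfort on an assumed deficit of 20 to 30 points. On those terms the shift is modest at the planned 3.4% loss and becomes material if Test loss approaches 10%. With equal, similar loss it is about zero. The change is a cheap improvement, worth making because the current check cannot serve its stated purpose.

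**What to change.** In SAP 7.6 and 10.1, replace the optional sampling with a mandatory sensitivity analysis on all randomised subjects, including those with no two-week value. Baseline CLUE is collected before lens assignment, so the comfort covariate should be available.

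1. **Comfort and logMAR.** Sample missing values with a shift toward worse for subjects who discontinue for lens-related reasons: lower for CLUE comfort, higher for logMAR, where a lower value is better. Vary the shift by arm and report the shift at which non-inferiority is lost.
2. **Bright light.** Count subjects who discontinue for unsatisfactory vision or lens discomfort as not satisfied, and vary the assumed response for other missing subjects. The composite is kept this narrow because a handling or adverse-event exit says little about vision in bright light. A subject stopped at fitting may never have worn the lens in such light, which is why this belongs in a sensitivity analysis.
3. **Reporting.** Tabulate loss by arm and reason from one consistent list. Handling difficulty appears in SAP 9.1 but not in SAP 11.4.

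The primary PP analysis, withdrawal rules, visits and sample size do not change. The cost is a few more MCMC runs and one aligned reason list. The downside is that the sensitivity result may look less favourable.
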